### 12.6.1. Constant-Murley Score

The Constant (Constant 2008) and adjusted Constant score (Constant 1986) will be summarized as part of the primary endpoint and as an inferential secondary endpoints. The Constant score is calculated as the sum of the following components:

- Average of 2 pain scores (15 points max):
  - Pain in shoulder normal activity: No=15, mild=10, moderate=5, severe=0
  - Linear 0-15 scale, where 0=no pain and 15=max pain, scored as the inverse of the scale: 15-(scale score); e.g., 15-0=15 (no pain contributes 15), 15-1=14,...,15-15=0 (max pain contributes 0).
- Sum of 4 activities of daily living questions (20 points max):
  - Occupation or daily living limited by shoulder: no=4, moderate=2, severe=0
  - Leisure and recreational activities limited by shoulder: no=4, moderate=2, severe=0
  - Sleep disturbed by shoulder: no=2, sometimes=1, yes=0
  - Highest level can use arm for reasonably painless activity: waist=2, xiphoid=4, neck=6, top of head=8, above head=10
- Sum of 4 ROM measure (40 points max):
  - o Forward flexion: 0-30=0, 31-60=2, 61-90=4, 91-120=6, 121-150-8, >150=10
  - o Abduction: 0-30=0, 31-60=2, 61-90=4, 91-120=6, 121-150-8, >150=10
  - External rotation: 2 points for each location reached (up to 10 points total)
  - Internal rotation: lateral thigh=0, buttocks=2, lumbrosacral junction=4, waist=6, 12th dorsal vertebra=8, interscapular region=10
- Power score (25 points max):
  - Average of 3 pulls (maximum of 25 pounds per pull) [Note: Statistician to verify pull was performed since some may say no but have 0 recorded.]

The average of three pulls were planned to be used to determine the strength component of the Constant score. In order to minimize missing data, the score will be calculated as long as at least one pull recorded. The average of the available pulls (1-3) will be used in the calculation.

Any combination of missing values that equate to a potential of >20 points would be excluded. For example, missing strength testing excludes a patient (if the subject was unable to complete the strength test then this would not exclude the patient); missing more than two of the ROM measures would exclude a patient; missing pain and one ROM test would exclude a patient, etc. For questionnaires missing partial data but not meeting the

exclusion threshold, missing responses are assumed to be worst case (contribute 0). Point details are as follows:

- Pain (up to 15 points): only one of the two pain scores is required
- Activities of daily living: 4 questions; total of 20 points
- ROM: 4 tests; 10 points each
- Strength: Strength contributes 25% of the total score (>20% threshold).

The constant score adjustments will be made using Constant adjustment values in Table 1:

Age (y)	Male	Female
21-30	98	97
31-40	93	90
41-50	92	80
51-60	90	73
61-70	83	70
71-80	75	69
81-90	66	64
91-100	56	52

Table 1: Constant Score Adjustments

Apply the adjustment by dividing the score by the factor in the table, then multiplying by 100.

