### **10. Sample Size Considerations**

Statistical considerations for powering the primary endpoint include the following:

- 80% power with a one-sided 0.025 level of significance
- Non-inferiority test of one proportion
- 10% non-inferiority margin, and performance goal of 85%
- Assumed investigational system success rate of 85%
- Attrition rate of 15%

The sample size for this endpoint was calculated using SAS (Version 9.3) under a one-sided z-test of a binomial proportion. The minimum required sample size is estimated using the above list of statistical considerations. The resultant sample size under these assumptions is 133 subjects. With 15% attrition, 157 total subjects with an attempted implant are needed. Up to 190 subjects may be enrolled to account for pre and intra-operative screen failures. Enrollment will stop once 157 subjects have had an implant attempt.

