### 12.5. Primary Effectiveness Analysis

### 12.5.1. Primary analysis

The primary endpoint is the rate of patient success at 24 months. A subject is a success at 24 months if:

- Their change in Constant score is  $\geq 17$  and
- They did not have revision surgery; and
- There is no radiographic evidence of system disassembly or fracture, and
- They did not have a system-related serious adverse event.

Subjects that undergo revision surgery within 24 months will be considered a primary endpoint failure at the time any component of the system is revised.

If a subject is missing the 24 month radiographic evidence assessment or Constant score component of the composite endpoint and did not have a system-related SAE or revision surgery, they will be excluded from the primary analysis due to inability to claim success or failure.

Subjects in whom an implant was attempted but the implant was unsuccessful will be included as failures in the primary analysis, regardless of the availability of 24 month radiographic evidence assessment or Constant score.

The presence of radiographic evidence of system disassembly or fracture will be assessed by independent radiologists. Discrepancies among the independent evaluations will be settled by majority rule. If the radiologists are unable to assess or the image wasn't available at 24 months, this will be considered missing data and the subject will be excluded from the primary analysis.

The non-inferiority of the test system to the performance goal will be evaluated using the 95% CI for the observed test system success rate. The study will be considered a success if the lower bound of the confidence interval is greater than 75% (85% - 10%).

The number of subjects who are successes (X) for each of the 4 individual components of the composite success endpoint, along with the number evaluated (N), will be summarized at 12 and 24 months as (X/N) and displayed with the overall success endpoint results based on data up to 12 and 24 months.

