### 12.5.2. Sensitivity Analysis

Two separate sensitivity analyses will be completed on the primary endpoint, outlined below:

- 1) The primary effectiveness analysis will be repeated under the assumption that all subjects with missing endpoint data were successful.
- 2) The primary effectiveness analysis will be repeated under the assumption that all subjects with missing endpoint data were failures.
- 3) The primary effectiveness analysis will be repeated using multiple imputation for missing endpoint data. The covariates that may (list not all-inclusive) be included in the multiple imputation process are: age, gender, treated shoulder, arthritis diagnosis, Constant score (baseline and 12 month), and BMI.

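### Some subjects with a partial Constant score are treated as unknown although their recorded items already settle the 17-point change, so the all-success and all-failure analyses are looser than they need to be

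*SAP*

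**What the plan says.** The primary composite (protocol 5.1, SAP 12.5.1) uses the Constant score only through a yes/no criterion: a change of at least 17 points from baseline.

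SAP 12.6.1 sets the scoring rule: "Any combination of missing values that equate to a potential of >20 points would be excluded". It names a missing strength test as sufficient, because "Strength contributes 25% of the total score (>20% threshold"). When 20 points or fewer are missing, the missing items score 0 and the total is kept.

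SAP 12.5.1 says that subjects without a 24-month Constant score, and with no revision or system-related SAE, are left out: "they will be excluded from the primary analysis due to inability to claim success or failure". Unsuccessful implant attempts stay in as failures.

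SAP 12.5.2 repeats the analysis with all missing subjects as successes, then on the assumption that "all subjects with missing endpoint data were failures", then with multiple imputation. The possible imputation covariates named include the baseline and 12-month Constant scores. The recorded 24-month items are not named, although the list is stated to be incomplete.

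**The concern.** A score can be too incomplete to report as a number and still be complete enough to answer the 17-point question. With strength missing, 75 of the 100 points are observed, and they may place the change wholly on one side of 17. The SAP's reason for exclusion, that success or failure cannot be claimed, is then untrue for the Constant component. If the component has certainly failed, the composite has failed too.

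The consequence falls on the sensitivity analyses. The all-failure run counts some subjects as failures who cannot be Constant failures, and the all-success run counts some as successes who cannot be. A lower bound that is needlessly low could make a sound primary result look fragile, and the reverse holds for the upper bound.

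**Working it through.** **Planned sample size.** Inputs from SAP section 10: "80% power with a one-sided 0.025 level of significance"; "10% non-inferiority margin, and performance goal of 85" percent, so the null rate is 0.75; "Assumed investigational system success rate of 85" percent; "Attrition rate of 15" percent.

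n = [(1.960·√(0.75·0.25) + 0.842·√(0.85·0.15)) / 0.10]² = 132.07, rounded up to 133. Then 133/0.85 = 156.5, rounded up to 157. Both match the SAP.

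**Bounds with 24-month strength missing.** Let B be the full baseline score and O the recorded 24-month points without strength. Strength lies between 0 and 25 (SAP 12.6.1), so the change lies between O − B and O − B + 25.

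- Constant component certainly met: O ≥ B + 17.
- Certainly failed: O + 25 − B < 17, that is O < B − 8.
- Undetermined: B − 8 ≤ O < B + 17.

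| B | O | Possible change | Status |
|---|---|---|---|
| 35 | 60 | 25 to 50 | certainly met |
| 35 | 52 | 17 to 42 | certainly met |
| 35 | 51 | 16 to 41 | undetermined |
| 60 | 51 | −9 to 16 | certainly failed |

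Under the current rule all four are unknown, absent a revision or system-related SAE.

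**Bounds with baseline strength missing.** With b the recorded baseline points and S the full 24-month score, the change lies between S − b − 25 and S − b. The component is certainly met if S ≥ b + 42 and certainly failed if S < b + 17.

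**How often the status is settled.** The documents give no mean or SD for the Constant change, so this part rests on assumed distributions, for subjects missing only 24-month strength.

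- With 85% reaching 17 points, SD of change 16 to 24, mean strength 8 to 16 and correlation of strength with change 0.3 to 0.6: 52–78% certainly met, 1–7% certainly failed, 19–45% undetermined.
- A second set of assumed distributions, restricted to those where 84–85% reach 17 points: about 60–75%, 1–2% and 24–38%.
- The second set without that restriction (about 68–90% reaching 17 points): 29–80%, 1–7% and 19–65%.

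**Effect on the extreme analyses.** With all 157 implant attempts in the denominator, each settled subject moves a rate by at most 1/157 = 0.64 points. If six subjects were affected (an assumption), the first set gives 6 × 0.52 = 3.1 to 6 × 0.78 = 4.7 certain Constant successes. The all-failure rate would then rise by up to 3.1/157 = 2.0 to 4.7/157 = 3.0 points, provided that these subjects also meet the other components. Certain failures would number 0.06 to 0.42, lowering the all-success rate by less than 0.3 points.

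**Why settled subjects should not simply join the primary analysis.** Take 133 complete subjects at 85% (113.05 successes) and six more missing strength at random, hence 5.1 expected successes. Suppose that 4.4 of the six are settled, 4.2 of them as successes.

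- Complete cases only: 113.05/133 = 85.0%.
- All six, if they could be seen: 118.15/139 = 85.0%.
- Settled ones only added: (113.05 + 4.2)/(133 + 4.4) = 117.25/137.4 = 85.3%.

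Across the first set of assumptions, with strength SD 5 also assumed, 90–99% of the settled subjects are successes and 35–76% of the undetermined. The rate moves from 85.0% to about 85.2–85.5%.

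**The case against.** **The trigger is narrow.** This stands. Strength is required at baseline and 24 months and is optional only at 3 and 6 months (protocol 7.4). One pull is enough. A subject unable to do the test is not excluded under SAP 12.6.1, and one who cannot reach the test position scores zero under protocol Appendix 2. Revisions, system-related SAEs and failed implants already count as failures. A missed visit leaves no 24-month items to bound. What mainly remains is an attended visit at which strength was not done or not recorded. Neither document gives a count, and the 15% attrition allowance gives some protection for power.

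**The 20-point limit is a prespecified scoring convention, similar to the one for ASES.** This also stands. It is reasonable for reporting a mean score and need not match the 17-point criterion. It does not follow that a voided score leaves the yes/no question open.

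**The all-failure run is meant to be the most conservative.** It remains a worst case after the change: every subject who could be a failure given the recorded data is still counted as one.

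**Stronger readings.** A reader might infer that the two extreme analyses are invalid. They are not: the truth still lies between them, and they are only wider than necessary. A reader might also infer that the primary rate is biased by the exclusion. If strength is missing at random, the complete-case rate is unbiased. It would favour the device if strength were skipped in poorly functioning shoulders, but nothing in the documents shows that. Nor do they support adding only the settled subjects to the primary analysis, which would introduce a bias where random missingness gives none.

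**Conclusion.** The point holds as a modest improvement to the sensitivity analyses. The logic of the bounds needs no distributional assumption: under SAP 12.6.1 and 12.5.1 some subjects are called unknown whose Constant result is already determined. The cost is at most 0.64 points of unnecessary width per settled subject at n = 157.

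How many subjects this concerns cannot be known from the documents and is probably small. The share of affected subjects who are settled rests on assumed score distributions. A certain Constant success is a composite success only if the radiographic and other components are also met; a certain Constant failure is a composite failure without further conditions.

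**What to change.** In SAP 12.5.2, before the all-success and all-failure analyses, compute two values for every subject whose Constant score is void but who has recorded items:

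- Lowest possible change: missing 24-month items at 0, missing baseline items at their maximum.
- Highest possible change: the reverse.

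Then:

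- If the highest change is below 17, count a failure.
- If the lowest change is 17 or more, count the Constant component as met, and the composite as a success only if the other components are met.
- Apply the all-success or all-failure assumption only to partial scorers whose values straddle 17. Subjects whose status is missing for another reason are handled as now.
- In the multiple imputation, impute the missing items conditional on the recorded 24-month items, so that imputed status respects these limits.

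Leave the primary complete-case analysis as it is, and report beside it how many excluded subjects are certain Constant successes and how many are certain failures. Keep the 20-point rule for the secondary mean Constant score.

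The cost is a short paragraph in the SAP and a few lines of code for the bounds, plus item-level specification of the imputation. No new data are needed. The change should be made before outcomes are seen.

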#### 12.6.2. ASES Score

The maximum shoulder score is 100 points and is derived by the following formula (Michener 2000):

 $[(10 - VAS \text{ score for pain}) \times 5] + [(5/3) \times Cumulative ADL \text{ score}]$ 

in which the VAS score ranges from 0 to 10 (cm) and the 10 ADL questions are scored as: 0='unable to do', 1='very difficult to do', 2='somewhat difficult to do', 3='not difficult'. To account for partially missing questionnaires, the following rules will be applied:

- Pain question required. Rationale: it is worth up to 50 points of the 100 point calculation.
- Up to 4 of the 10 patient questionnaire questions can be missing; if 4 or fewer are missing the missing response(s) is assumed to be worst case (contribute 0). Rationale: 4 patient questionnaire answers contribute 20% of the total score.

# 12.6.3. EQ-5D Scoring

The EQ-5D will be summarized using EQ-5D-5L descriptive score and EQ VAS score (http://www.euroqol.org/).

The EQ-5D-5L score will be derived by recoding the 5 dimensions to a single-digit numeric value based on the level they indicated for that dimension. These digits will be concatenated (in the order of the actual dimensions) together to obtain a 5-digit number describing the subjects state of health. This number will used to allocate a score for each subject using a downloaded spreadsheet from aforementioned website. Subject scores will be determined from the spreadsheet based on their 5-digit number. Subjects must have all 5 dimensions in order to obtain an EQ-5D-5L score.

The EQ VAS score is derived from the respondent's self-rated health on a 20 cm vertical, visual analogue scale with endpoints labelled 'the best health you can imagine' and 'the worst health you can imagine'. This information is used as a quantitative measure of health as judged by the individual respondents.

## 12.7. Additional Secondary Endpoints

The following secondary endpoints will be presented using descriptive statistics only. Analyses will be performed on the ITT population, using all available data.

- Adverse events
- Revision rate
- Level of satisfaction with the shoulder
- X-ray data: glenohumeral joint space width, glenoid osteophytes, glenoid morphology, glenoid erosion, and glenoid wear, humeral component radiolucency, osteolysis, migration, subsidence, subluxation, humeral head integrity, acromial humeral distance, anatomic fracture, and additional observations

The revision rate and radiographic data will be summarized and qualitatively compared to a subset of data from the Tornier Aequalis Post-Market Outcomes Study and data reported in literature. This will be included in the final clinical report.

Note that safety is included in the primary composite endpoint and also as a descriptive secondary endpoint. See section 12.10 below for additional details on planned safety analyses.

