7.1 Overview of Study Design

Figure 5 outlines the study overview and subject flow. Subjects who are screened and provided informed consent are considered enrolled and will complete a pre-operative baseline study assessment.

Subjects who are enrolled and have a successful implant attempt (implant stable through wound closure) will have study assessments at 2 weeks, 3 months, 6 months, 12 months, 24 months, and annually thereafter (until the last subject with an implant attempt completes their 24 month visit or is determined lost to follow-up) following surgery. Subjects will exit the study after the last subject with an implant attempt completes their 24 month visit or follow subjects their 24 month assessment unless it is determined, at the end of the study, to follow subjects long-term.

Subjects who are enrolled and have an unsuccessful implant attempt (attempt to implant the Pyrocarbon Humeral Head was not successful during the index procedure) will have annual post-op visits at 12 and 24 months in order to collect any available safety information. This also includes subjects who are excluded due to excessive glenoid reaming performed with the intent of implanting the Pyrocarbon Humeral Head. Subjects will exit the study after the 24 month assessments are complete.

Subjects who are enrolled but become screen failures intra-operatively (prior to the implant attempt) will have the reason for screen failure documented and then will be followed annually to collect any available safety information. Subjects will exit the study after the 24 month assessments are complete.

Subjects who are enrolled but become screen failures pre-operatively (prior to surgical procedure) will have the reason for screen failure documented then will be exited from the study.

If any component of the investigational system is revised, the subject will follow the planned follow-up visits. If any component of the investigational system is permanently explanted during the course of the study, the subject will only have annual post-op visits at 12 and 24 month to gather available safety information. Revisions and explants are defined in section 7.7

[figure not shown]

Figure 5: Study Overview

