7.6.10 Follow-up: Revisions

If a subject has revision surgery, the subject shall remain in the study and complete all required follow-up visits.

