7.6.11 Follow-up: Explants

Subjects who have the Pyrocarbon HH explanted shall remain in the study and complete annual follow-up visits to gather available safety data

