7.7 Additional Data Collection

Subjects may call or visit the investigative site at times other than for required study visits. It is only required to notify Tornier if the visit or phone call is associated with an adverse event, revision, device explant, reoperation, device malfunction, subject death, or study exit. Data associated with these events must be documented and reported in the database on the associated eCRFs.

Revision and Device Explants

A revision is a procedure that adjusts or in any way modifies or removes any component of the original implant configuration, with or without replacement of a component, after the initial surgery. A revision may also include adjusting the position of the original configuration.

An explant is a revision that includes permanent removal of any system component. If a subject has a revision that includes an addition of a glenoid component (revision to TSA) the Pyrocarbon humeral head must be permanently explanted.

All explanted system components, including the Pyrocarbon HH devices and stems, must be returned to Tornier for analysis per the system retrieval and analysis protocol in Appendix 4.

Reoperation

A reoperation is any invasive procedure to the affected shoulder that does not include removal, modification or addition of any components to the original implant configuration (e.g., drainage of a hematoma at the surgical site). Subjects will not be considered a failure solely due to a reoperation and will follow their original follow-up schedule.

Device Malfunction

All failures and malfunctions of the implant system must be reported to Tornier as soon as possible. In the event of a system malfunction, every effort must be made to return the suspected system to Tornier for analysis.

Death

During the study, all deaths must be reported to the Sponsor within 10 working days of the study personnel's knowledge of the death. A copy of death records, medical records for the events that led to the subject's death, death certificate (if available) and an autopsy report (if performed) must be sent to the Sponsor as soon as they become available.

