Subjects who are enrolled but become screen failures intra-operatively (prior to the implant attempt) will have the reason for screen failure documented and then will be followed annually to collect any available safety information. Subjects will exit the study after the 24 month assessments are complete.

Subjects who are enrolled but become screen failures pre-operatively (prior to surgical procedure) will have the reason for screen failure documented then they will be exited from the study.

If any component of the investigational system is revised, the subject will follow the planned follow-up visits. If any component of the investigational system is permanently explanted during the course of the study, the subject will only have annual post-op visits at 12 and 24 month to gather available safety information. Revisions and explants are defined in section11.2.

	Baseline (Pre-op)	Day of Surgery (DOS)	Post-op Follow-up (5-21 days)	Follow-up 3M (69-111 days)	Follow-up 6M (159-201 days)	Follow-up 12M (323-407 days)	Follow-up 24M (688-772 days)	Follow-up Annual (if needed)
Demographics, Medical History and Indication	х							
Intraoperative Data		Х						
Subject Questionnaire	Х			Х	Х	Х	Х	х
Range of Motion	Х			X*	X*	Х	Х	Х
Strength Test	Х			X*	X*	Х	Х	Х
Pain Medications	Х	Х	Х	Х	Х	Х	Х	Х
Adverse Event Assessment		Х	х	Х	х	Х	Х	X
X-ray	Х		Х		Х	Х	Х	Х

Data collection schedule is as follows:

\*Optional

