# 11.2. Missing Data and Censoring

The impact of missing data for the primary efficacy endpoint will be assessed by a sensitivity analysis. See the primary endpoint section for details.

No imputation for missing data will be performed on secondary endpoint data; i.e., patients missing the endpoint result at a visit or prematurely withdrawing prior to the time point at which the endpoint is measured will be excluded from the analysis of that endpoint.

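### Unless the Imaging Charter says otherwise, a shoulder converted to total shoulder arthroplasty for glenoid erosion drops out of the 24-month erosion summary, and the SAP has no table of revisions by reason

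*SAP*

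**What the plan says.** SAP 12.7 covers glenoid erosion with the other X-ray findings: "The following secondary endpoints will be presented using descriptive statistics only. Analyses will be performed on the ITT population, using all available data". It then plans a qualitative comparison of the revision rate and the radiographic data with the Aequalis subset and the literature. Under SAP 12.1 a categorical grade is reported as counts and percentages.

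SAP 11.2 rules out imputation for secondary endpoints and states that "patients missing the endpoint result at a visit or prematurely withdrawing prior to the time point at which the endpoint is measured will be excluded". This exclusion applies endpoint by endpoint.

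Protocol 7.7 says that with "a revision that includes an addition of a glenoid component (revision to TSA) the Pyrocarbon humeral head must be permanently explanted". Protocol section 3 describes TSA as having an artificial component on the glenoid side as well as the humeral side. After an explant, Protocol 7.1 provides that "the subject will only have annual post-op visits at 12 and 24 month to gather available safety information", and Protocol 7.6.11 keeps such subjects in annual follow-up.

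Conversions are recorded in several places. They are primary endpoint failures (SAP 12.5.1), events in the Kaplan-Meier revision rate (SAP 12.6) and entries in the secondary-surgery table (SAP 12.11). That table sorts by type of procedure: revision, removal, reoperation or other. Adverse events are tabulated by term. Protocol Appendix 4, section 5, collects the reason for device removal on the revision/explant form. Protocol 7.3 refers to an Imaging Charter for further detail on X-ray reading.

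**The concern.** Protocol 10.2 lists glenoid erosion among the anticipated complications and says that such complications may lead to revision. Protocol 11.3 gives reduced wear of the patient's own glenoid, relative to cobalt-chrome heads, as the potential benefit of the device. The erosion summary is therefore the descriptive result closest to the claimed advantage.

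The shoulder in which that benefit failed most clearly is one that eroded until the glenoid had to be resurfaced. After conversion there is no native glenoid to grade at 24 months. The reading is missing because of the outcome being measured, and the available-data rule drops the subject. The SAP gives neither a rule for this case nor a table from which a reader could see how many revisions were for erosion.

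What is at stake is how the erosion figure reads in the clinical report. No hypothesis test depends on it, and the endpoint's descriptive status is not the complaint.

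**Working it through.** **Inputs from the documents**

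- Evaluable sample: 133 (SAP 10). It reproduces from a one-sided z-test of 0.85 against 0.75: n = (1.960 × √(0.75 × 0.25) + 0.842 × √(0.85 × 0.15))² / 0.10² = 132.07, rounded up to 133. With 15% attrition, 133 / 0.85 = 156.5, rounded up to 157.
- Historical 24-month revision rate: 10/191 = 5.2% (SAP 12.6).
- Revision limit: 5.2% + 8% = 13.2% (SAP 12.6).

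**Assumptions.** The documents give no erosion rate and no breakdown of revisions by cause.

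- q is the share of shoulders still read at 24 months that fall in the worse erosion category, taken as 0 to 30%.
- k is the number converted to TSA for erosion. All k are assumed to belong in the worse category and to have no 24-month grade.
- 133 is an illustrative denominator. It is the evaluable number for the primary endpoint, which includes unsuccessful implants, and is not a count of graded films.

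**Formula**

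- Figure shown: q
- Figure with conversions counted: (q × (133 − k) + k) / 133
- Understatement: (1 − q) × k / 133

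This cannot be negative, so leaving out erosion conversions can only lower the figure.

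**Values of k**

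- Revisions of any type at the historical rate: 10/191 × 133 = 6.96, about 7.
- Revisions at the 13.2% limit: 0.132 × 133 = 17.6, taken as 17.
- If 10% or 25% of revisions at the historical rate were erosion conversions (assumed shares), the expected k is 0.10 × 6.96 = 0.7 or 0.25 × 6.96 = 1.7. Hence the rows for one and two.

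| Erosion conversions k | q = 30% | q = 0 |
|---|---|---|
| 0 | 0 | 0 |
| 1 | 0.7 × 1/133 = 0.53 points | 1/133 = 0.75 points |
| 2 | 0.7 × 2/133 = 1.05 | 2/133 = 1.50 |
| 7 (every revision, 5.2% rate) | 0.7 × 7/133 = 3.68 | 7/133 = 5.26 |
| 17 (every revision, 13.2% limit) | 0.7 × 17/133 = 8.95 | 17/133 = 12.78 |

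The last row is a stress case. SAP 12.6 requires the upper confidence bound to lie below 13.2%, so a trial observing 13.2% would already fail its revision test.

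**Example with k = 2.** As observed, 13/131 = 9.9% (exact 95% CI 5.4 to 16.4). With both conversions counted, 15/133 = 11.3% (6.5 to 17.9). The intervals overlap heavily.

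**The missing link.** Set side by side, SAP 12.11 tabulates secondary surgery by procedure type and adverse events by term, SAP 12.6 counts revisions of any cause, and SAP 12.7 summarises erosion among shoulders with a reading. None of them uses the reason for removal recorded under Appendix 4.

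**The case against.** The strongest reply is that a replaced glenoid has no erosion grade, so a summary of the shoulders still readable describes those shoulders correctly. Each conversion is visible as a primary failure, a revision event and a timed secondary-surgery entry. Earlier films stay in their own visit summaries. Erosion may appear as an adverse event term, and returned components receive a cause-of-failure analysis. SAP 12.7 pairs the revision rate with the radiographic data in one comparison, and with a handful of cases a narrative would serve. All of this is right and keeps the point small. It does not supply the count of revisions for erosion, or show beside the erosion percentage how many shoulders left it for that reason.

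Two further replies limit the certainty. The Imaging Charter may already say how a replaced glenoid is coded. SAP 12.7 names no visit, so the 24-month summary is inferred from the visit schedule and from the wording of SAP 11.2. Both conditions stand.

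Some stronger readings are tempting but unsupported:

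- A reader might infer that the erosion comparison favours the device. The documents do not show this, because Aequalis and the published series may also lack readings after conversion.
- A reader might treat the 5.2% revision rate as an upper limit on the effect. It is a historical estimate, and the 13.2% limit allows a larger gap.
- A reader might extend the point to every permanent explant. Although "permanently explanted during the course of the study, the subject will only have annual post-op visits at 12 and 24 month", X-ray is scheduled at both visits (Protocol Table 3), and an explant that leaves the native glenoid in place can still be read.

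**Conclusion.** The concern holds in conditional form. If the Charter has no coding rule and erosion-driven conversions occur, SAP 11.2 and 12.7 together remove those shoulders from the 24-month erosion figure, and the figure is then too low. The likely size is small: about half a point to one and a half points for one or two conversions. It reaches 4 to 5 points, or 9 to 13 in the stress case, only if every revision were for erosion. These sizes rest on assumed values of q and k and on 133 as a convenient denominator. With no such conversions the gap is nil.

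The primary conclusion and the revision-rate test do not change. The absence of a revision-by-reason table is a separate gap in the SAP as written, and a film-reading charter would not be expected to fill it. This is an inexpensive improvement worth considering.

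**What to change.** 1. In SAP 12.11, tabulate revisions and explants by the recorded reason for removal, with revisions that replace the glenoid as their own row.
2. In SAP 12.7, show the number converted to TSA, and the number converted for erosion, beside the number read at 24 months. Keep the as-observed erosion summary.
3. Add one supplementary line that counts conversions recorded as due to glenoid erosion in the worst erosion category. If the Imaging Charter already has a coding rule for replaced glenoids, cite it in SAP 12.7 instead.

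The cost is SAP wording and a few table rows. Scheduled films and the reason for removal are already collected, so no new visit, film or form is needed. There are two downsides. The supplementary line relies on a reason recorded by an unblinded site and not by the core lab, which is why it should sit beside the as-observed summary and not replace it. It may also give a less favourable erosion figure.
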